3.5 Secondary endpoints

- Long term quality of life profile;
- Reduction in pain intensity (PI-NRS);
- Time to worsening of the pain and use of rescue medication for pain (MQS III-R);
- Global perceived effect (GPE);
- Effect on mood (Hospital Anxiety and Depression Scale);
- Quality of sleep (NRS and ISI);
- Percentage of patients without systemic drug related side effects (dizziness, fatigue, vertigo, somnolence, headache, blurred vision);
- Time to discontinuation of the study drug and proportion of patients stopping the drug;
- Participation in activities (Utrecht Work Engagement Scale-9);
- Impact of pain on functioning (interference BPI);
- Work Productivity and Activity Impairment (WPAI: Neuropathic Pain, v2.2, Belgium);
- Neuropathic Pain Symptom Inventory (NPSI).

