10.3.2 Primary outcome analysis

The primary outcome EQ-5D-5L at 6 weeks will be compared between the 3 treatment arms in first instance using a linear regression model with treatment as a predictor and correction for quality of life at baseline. All patients in the study will be used in an intention-to-treat (ITT) analysis.

Patients who withdraw from the study medication are offered a different treatment option of topical or systemic treatment respectively. Following standard care practice patients on the pregabalin arm will be offered an alternative systemic drug (gabapentin) and patients on the topical arm will be offered a different topical drug (failing treatment with lidocaine 5% medicated plasters will be treated with capsaicin patches and otherwise) Cross-over between topical and systemic treatment is not allowed to maximally preserve the treatment

effect between the two methods. Non-compliers and withdrawals are followed up according to the protocol. Their data will be collected in the same way as for the adherers and in the analysis they will be considered in the initially randomised treatment arm.

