10.3.3 Secondary outcome analysis

- Different sensitivity analyses will be done to evaluate the treatment effect at 6 weeks. Confounders like the use of rescue medication, the 3 stratifying variables (sensory disturbances such as hyperalgesia/allodynia, spontaneous positive sensory disturbances and duration of pain) and some other known confounders (gender, level of education, family situation) will be added to the linear regression model.
 - A linear mixed model using all quality of life measurements over the 26 weeks with subject as random effect will improve the precision on the estimated treatment effect at 6 weeks. This complex model will be expanded by including site as a random effect and possible confounders will also be added to this model as fixed effects. From the linear mixed model the long term profiles of the treatments over the 26 weeks can be determined and using time as a categorical variable in this model will allow different linear evolutions from one time point to another.
- For each patient, an area under the curve including all quality of life
 measurements will be calculated using the trapezium rule and compared
 between the different treatment arms using linear regression. The area under
 the curve can be seen as a summary measure summing up initial treatment
 response or lack off and the effect of any rescue medication during follow-up.
- A similar analysis will be done for the subgroup of patients who adhered to the protocol in a per protocol analysis.
- Linear regression at 6 and 26 weeks will be performed to compare the pain intensity between the 3 treatment arms. Changes over time will be analyzed using linear mixed effect models.
- The use of rescue medication using MQS-III will be evaluated at 6 and 26 weeks using linear regression. Changes over time will be analyzed using linear mixed effect models.
- The time to worsening will be studied in a time-to event analysis comparing the different treatment arms. Two different events of worsening will be considered:
 - The first time the patient experiences a 30% increase in MQS-III score
 - This implies that patient has either significantly increased the use (number of intakes) of the rescue medication or has started taking analgesics of a higher level (WHO step ladder)
 - The first time the patient has a worsening of the pain in terms of 2 units rise on the pain intensity (numeric rating scale NRS) scale compared to the previous assessment.

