- The percentage of systemic drug-related side effects will be evaluated at 6 and 26 weeks using Chi-square test or Fisher's exact test. The evolution of the percentage of systemic drug-related side effects over time will be analyzed using a generalized linear mixed effects model using the clinical visit data and

the self-reported patient data.

- Discontinuation of study drug or study withdrawal: the percentage of study
 withdrawal will be compared after 6 and 26 weeks with a Chi-square test or
 Fisher's exact test whatever is appropriate based on assumptions. The time to
 discontinuation will also be studied in a time-to event analysis comparing the
 different treatment arms. The self-reported patient data will be used for this.
- Global perceived effect (GPE), effect on mood (Hospital Anxiety and Depression Scale), quality of sleep (Sleep-NRS and ISI), participation in activities (Utrecht Work Engagement Scale-9), impact of pain on functioning (interference – BPI), and Work Productivity and Activity Impairment (WPAI-Neuropathic Pain) will be compared at 26 weeks using linear regression and over time using linear mixed models.
- Similar to the primary outcome the treatment effect on the secondary outcomes will be estimated in a model with adjustment for confounders and including site as a random effect

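### The secondary linear regressions and the EQ-5D-5L AUC regression state no adjustment for the outcome's own baseline value, which gives up precision that the trial could have for free

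*Protocol*

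**What the plan says.** Section 10.3.2 defines the primary model as a linear regression with "treatment as a predictor and correction for quality of life at baseline".

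Section 10.3.3 sets out the secondary models:

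- **Pain intensity.** "Linear regression at 6 and 26 weeks will be performed to compare the pain intensity between the 3 treatment arms". A second sentence adds: "Changes over time will be analyzed using linear mixed effect models". MQS-III is treated in the same two ways.
- **EQ-5D-5L AUC.** For each patient the area over all quality-of-life "measurements will be calculated using the trapezium rule and compared" between arms by linear regression. The protocol explains its purpose: "The area under the curve can be seen as a summary measure summing up initial treatment response", together with the effect of any rescue medication.
- **GPE, HADS, sleep NRS, ISI, UWES-9, BPI interference, WPAI.** These "will be compared at 26 weeks using linear regression and over time using linear mixed models".
- **Closing bullet.** It likens the secondary outcomes to the primary one and speaks of a model adjusted for confounders, with site as a random effect.

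The confounders named in 10.3.3 are rescue medication, the three stratifying variables, gender, education and family situation. The baseline value of the outcome is not among them. Section 3.5 words the pain endpoint as a reduction on the PI-NRS.

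Section 7.6 collects a baseline for every one of these scales. Only GPE has none (section 7.8, footnote d). The minimisation factors in section 7.3 are site, hyperalgesia/allodynia, spontaneous sensory phenomena and pain duration, so neither baseline pain nor baseline EQ-5D-5L is balanced by design.

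**The concern.** Patients' scores before treatment usually predict their scores afterwards. A regression that leaves out the baseline score keeps that between-patient variation in its error term, and any chance difference between arms at baseline moves the estimate. The primary model avoids this; the secondary models, as written, do not say that they do.

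The AUC is the most exposed. It includes the measurement taken before treatment starts, on which treatment can have no effect, and every later value in it also correlates with that measurement. What is at stake is the width of the intervals for the pain, function and long-term quality-of-life comparisons. In an open-label trial there is also some value in settling the covariates in advance.

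**Working it through.** **The plan's own figure.** With effect 0.08, SD 0.240, two-sided alpha 0.025 and 80% power (section 10.1), the normal approximation is n = 2 × (2.241 + 0.842)² × (0.24/0.08)² ≈ 171.1, so 172 per arm. The exact t-test gives 172.35, so 173. Then 173/0.88 = 196.6, so 197 per arm and 591 in total. The stated sample size reproduces, and this point does not affect it.

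**Inputs.** The EQ-5D-5L schedule is weeks 0, 6, 10, 14, 18, 22 and 26 (section 7.8, footnote e). The correlation r between baseline and follow-up is not in the documents; 0.3, 0.5 and 0.7 are assumed. For the AUC, equal SDs and the same r between all visits are also assumed.

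**Single time point (pain, MQS-III, week-26 scales).** Residual variance with the baseline covariate, relative to the raw variance, is 1 − r². An effect that has 80% power with adjustment (two-sided 0.05) has power Φ(2.80 × √(1 − r²) − 1.96) without it.

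| r | Variance remaining | Variance removed | Power without adjustment |
|---|---|---|---|
| 0.3 | 0.91 | 9% | 76% |
| 0.5 | 0.75 | 25% | 68% |
| 0.7 | 0.51 | 49% | 52% |

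**AUC.** The trapezium weights are 3, 5, 4, 4, 4, 4, 2 (sum 26), so baseline has 3/26 = 11.5%. Divide the AUC by 26 and work in units of the single-visit SD:

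- covariance with baseline: c = 3/26 + (23/26) × r
- variance: v = r + (1 − r) × 102/676, where 102 is the sum of the squared weights (9 + 25 + 4 × 16 + 4)
- share of variance removed by adjustment: c²/v

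| r | c | v | Variance removed |
|---|---|---|---|
| 0.3 | 0.381 | 0.406 | 36% |
| 0.5 | 0.558 | 0.575 | 54% |
| 0.7 | 0.735 | 0.745 | 72% |

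If follow-up visits correlate 0.1 more with each other than with baseline, the shares removed are 31%, 49% and 67%.

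**Chance imbalance.** At 173 per arm, the standard error of the baseline difference between two arms is √(2/173) = 0.108 SD, a 95% range of about ±0.21 SD. Without adjustment a fraction r of the imbalance passes into a single-time-point comparison. The fraction c passes into the AUC, which at r = 0.5 is 0.56 × 0.21 ≈ 0.12 SD at the edge of that range.

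**Bias.** A null simulation of the unadjusted comparison (20,000 trials, 173 per arm, r = 0.5) gave a mean difference of 0.001 SD and a type I error of 4.98%. The unadjusted test is valid.

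No AUC power is given. The only SD in the protocol, 0.240, belongs to the change score. It equals the single-visit SD only if √(2(1 − r)) = 1, that is, at r = 0.5.

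**The case against.** **The protocol never says that baseline is left out.** The closing bullet of 10.3.3 likens the secondary models to the primary one, which is baseline-adjusted, and the confounders are described as additions to that model. On this reading the baseline term is already there. This stands in part: omission is inferred from silence, and the protocol should not be read as excluding the term. But the comparison is attached to confounders and a site effect, which the 10.3.2 model does not contain, so it does not clearly carry the baseline term over.

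**A separate analysis plan may settle it.** It may. Still, section 10.3 specifies these regressions itself and names covariates for them, so the term belongs in that list.

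**The mixed models already cover change over time.** They do so in part, for pain, MQS-III, the other scales and the EQ-5D-5L profile. They do not alter the fixed-time regressions, and the AUC comparison has only its regression.

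**A reader might infer that a patient's starting level is counted as treatment effect.** Individual examples suggest it. A patient going from NRS 9 to 6 ends worse than one staying at 4. A constant EQ-5D of 0.80 gives an AUC of 26 × 0.80 = 20.8, while a rise from 0.30 to 0.60 by week 6, then held, gives 6 × 0.45 + 20 × 0.60 = 14.7. But the plan compares randomised arms, not individuals. Starting levels have the same expectation in each arm, and the simulation shows no bias. For the same reason, analysing the pain level when the endpoint is called a reduction is not an error: both target the same between-arm difference, and the primary outcome is likewise a change analysed as a week-6 level.

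**Conclusion.** The point holds as a matter of precision, not validity. Section 10.3.3 names no same-scale baseline covariate for the secondary fixed-time regressions or for the AUC, although 10.3.2 names one for the primary outcome. If the term is indeed absent, the cost is about 9 to 49% of the variance at a single time point and about 36 to 72% for the AUC, together with exposure to chance imbalance. These sizes rest on assumed correlations of 0.3 to 0.7 and, for the AUC, on equal SDs and one common correlation. The direction of the gain does not depend on them. The documents do not support a claim of bias or of inflated type I error. The primary analysis and the figures of 173, 197 and 591 are untouched. This is a free improvement to secondary analyses rather than the correction of an error.

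**What to change.** Add one sentence to section 10.3.3: each secondary linear regression includes the baseline value of the same scale as a covariate, and the AUC regression includes baseline EQ-5D-5L, as section 10.3.2 does for the primary outcome; GPE is exempt because it has no baseline. With baseline in the model, the treatment coefficient for pain is the same whether the outcome is entered as the level or as the reduction, so the endpoint wording in section 3.5 can stay.

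The cost is that sentence and one degree of freedom per model. No new data are needed, since section 7.6 already requires these values before randomisation. If the closing bullet was meant to carry the baseline term over, the sentence simply confirms it.

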Planned Trial Period		21 months between first patient first visit and last patient last visit, 27 months till Clinical Study Report.				
	Objectives	Endpoints				
Primary	To determine if topical treatment significantly improves health-related quality of life compared to systemic treatment in adult patients suffering from localized neuropathic pain across a wide variety of etiologies (LNP), with a duration between 1 and 24 months.	Change in EQ-5D-5L from baseline to 6 weeks.				
Secondary	To compare the effectiveness in terms of pain relief between the treatment arms. To compare the	Reduction in pain intensity (PI-NRS), time to worsening of the pain (PI-NRS and NPSI) and use of rescue medication (MSQ III-R). AUC for EQ-5D-5L				
	effectiveness in different aspects of quality of life between the treatment arms.	measurements, global perceived effect (GPE), effect on mood (HADS), quality of sleep (NRS and ISI).				

To compare the drug Percentage of patients tolerance between without systemic drug related side effects. systemic and topical treatment. percentage of patients who discontinue the study drug. To identify the difference Impact of pain on between topical and functioning (Interference – systemic treatment in terms BPI), participation in of functional status of the activities (Utrecht Work Engagement Scale-9). patient. Work Productivity and Activity Impairment (WPAI). Interventions Topical treatment 1: lidocaine 5% medicated plaster (Versatis) Topical treatment 2: capsaicin 8% patch (Qutenza) Systemic treatment: pregabalin (generics) **Description of the** Topical treatment 1: daily administration of lidocaine 5% intervention or medicated plaster, during 12 consecutive hours, with a Formulation. Dose. maximum of 3 plasters at the same time. **Route of Administration** Topical treatment 2: capsaicin 8% patch, periodic of IMP administration upon reoccurrence of pain symptoms (mostly after 90 days), in a hospital setting during maximum 1 hour. Maximum number of patches is equal to the number needed to cover the painfull area. The surface of this area cannot be larger than 520cm2. Systemic treatment: pregabalin (oral administration), dose determined by up-titration in first 4 weeks with a maximum daily dose of 600mg.

FUNDING AND SUPPORT IN KIND

KCE is the only funder of this study. No commercial funding for this study.

ROLE OF STUDY SPONSOR AND FUNDER

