All patients suffering from such neuropathic pain conditions can be screened for participation in this trial. The inclusion of patients will in no way be limited to certain etiologies such as post-herpetic neuralgia (PHN), diabetic polyneuropathy (DPN) or post-radiation neuropathies. In most commercial clinical neuropathic studies inclusion of patients will be limited to one single etiology (in most cases either PHN or DPN), and in addition many inclusion and exclusion criteria will be imposed. This is NOT the case in this pragmatic trial where all adult patients suffering from localized neuropathic pain (= clearly defined by the international definition) can be included in this study. There are no exclusions based on concomitant medication, such as analgesics or anti-depressants. These drug classes are also included in the calculation of the medication quantification score (MQS-III-R score).

Patients can use their own rescue mediation since all analgesic medications will be recorded through the MQS-III score (online registration).⁵⁴⁻⁵⁷ As such, the investigators will be able to evaluate and objectivize the intake of analgesic medication (lower intake of analgesics will result in lower MQS-III scores during the course of the trial). In addition, investigators will be able to closely monitor the need for analgesic rescue medication (to treat acute episodes of pain or exacerbations of chronic painful neuropathy in our case).

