7 TRIAL PROCEDURES

7.1 Recruitment

7.1.1 Patient identification

Several routes of recruitment will be actively used in this trial.

- Patients will be recruited through the multidisciplinary pain centers. Recruited patients will both constitute of new patients, visiting the pain center for the first time, as well as patients who are already known in the center but never before had been treated with any of the analgesic medications investigated in this trial for similar painful conditions;
- Each multidisciplinary pain center has an official collaboration with the multidisciplinary algological teams of hospitals which do not have a pain center. This collaboration allows the pain centers to recruit patients coming from all acute hospitals in Belgium;
- In addition, patients will be recruited from an extensive network of general practitioners who work together with pain centers. GP's will be informed about this study through medical professional publications and scientific medical associations (e.g. Domus Medica). As such, GP's will be able to refer patients suffering from localized neuropathic pain syndromes directly to the participating pain centers.

Only members of the patient's existing clinical care team will have access to patient records to check if they meet the inclusion criteria.

No patient or disease registers will be used in this trial to identify potential participants. The clinical care teams of the different participating multidisciplinary pain centers will contact primary care physicians in their network to discuss the ongoing trial and ask their involvement to rapidly identify patients suffering from subacute to chronic localized neuropathic pain conditions and refer them to the pain centers for screening and possible inclusion in the trial. GP's will be able to consult the recently developed screening tool for localized neuropathic pain online, to allow a quick and easy pre-screening for presence of a localized neuropathic pain condition (this screening tool is also shown in the appendix 5 – Dutch and French versions of the screening tool will be made available for GP's.) ¹¹

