7.7 Trial assessments

The study comprises a screening period of maximum 21 days, randomisation (d-21 to d-1), a baseline visit at day 0 (start of treatment), a treatment period of 24 weeks and a post-treatment period of 2 weeks (24-26 weeks). Considering the pragmatic nature of the proposed trial clinic visits are kept to an absolute minimum.

The **clinical visits** take place at day 0 (V1), week 4 (V2), 12 (V3), 18 (V4), 24 (V5) and 26 (V6) which is comparable to a schedule which would be maintained in routine clinical care. A deviation of +/- 5 days is allowed for the clinical visits. The assessments made at these visits are (*routine care assessments are indicated in bold):*

- Documentation of the study intervention: number of patches (lidocaine and capsaicin), location, dosage used (pregabalin and gabapentin), compliance and discontinuation check
- Documentation of size of painful area
- Assessment of adverse events
- Assessment of systemic drug related side effects (e.g. dizziness, fatigue, vertigo, somnolence, headache, blurred vision) (not on baseline visit)

- · Concomitant medication use
- Only during V2 and V4 clinical sensory testing will be repeated (using the Boston Bedside Quantitative Sensory Testing Battery)

The majority of the assessments (patient reported outcomes and experiences) will be performed by making use of an online platform, enabling patients to complete the different assessments themselves without having to schedule a clinic visit. The use of the online platform will significantly reduce the work load for the patients involved in this study. Per regular weekly online assessment, the required time investment will not exceed 15 minutes. The online assessments on a monthly basis (n = 7 in total) will never require more than 30 minutes (which can be split over different moments).

Online assessments: weekly basis

A deviation of max. 48 hours is allowed for the completion The following procedures and assessments will be carried out:

- Assessment of reduction in pain intensity using PI-NRS
- Assessment of analgesic medication use (using MQS III)
- Quality of sleep: Sleep NRS
- Assessment of systemic drug related side effects (not collected at baseline)
- Discontinuation of study drug (not collected at baseline)
- Participation in activities: Utrecht Work Engagement Scale-9

Online assessments: monthly basis (baseline, week 6, 10, 14, 18, 22)

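### Pain worsening is measured against last week's score with no baseline anchor or confirmation, so slow deterioration is missed and rebounds count; the MQS-III event lacks a reference point and a clear scope

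*Protocol*

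**What the plan says.** Section 10.3.3 states: "The time to worsening will be studied in a time-to event analysis comparing the different treatment arms". It then defines two events.

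- **Pain:** the first "worsening of the pain in terms of 2 units rise on the pain intensity (numeric rating scale NRS) scale compared to the previous assessment".
- **Medication:** "The first time the patient experiences a 30% increase in MQS-III score". An explanatory line says that this reflects heavier use of rescue medication or a move to stronger analgesics.

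Section 7.7 places the pain score under "Online assessments: weekly basis" ("Assessment of reduction in pain intensity using PI-NRS"), and section 7.9 continues the weekly questionnaire through the two follow-up weeks. The previous assessment is therefore the previous week.

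On the scope of MQS-III, section 6 says that "all analgesic medications will be recorded through the MQS-III score". Section 8.1 labels protocol-supplied gabapentin as rescue medication.

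The trial summary gives a different basis for the endpoint: "time to worsening of the pain (PI-NRS and NPSI". Section 7.7 collects NPSI only with the monthly questionnaires.

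**The concern.** A time-to-worsening endpoint should tell the reader when a patient's pain became worse than it was at entry, or when control was lost. A week-to-week rule answers neither reliably. It ignores any decline made of 1-point steps, and it treats one upward fluctuation as a permanent event, even in a patient who is still much better than at baseline. Over about 26 chances, ordinary variation can produce an event in most patients who have not changed.

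The medication event has a different weakness. A 30% increase needs a reference score, and none is named. If that score is zero, the percentage does not exist, and the entry criteria in sections 6.1 and 6.2 do not require analgesic use. If study drugs are scored, titrating pregabalin or switching to gabapentin could itself register as worsening. Section 10.1 cites withdrawal from study medication of 18.6% on pregabalin, against 2.1% on capsaicin and 5.8% on lidocaine. An ambiguity over gabapentin would therefore not fall evenly on the arms.

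**Working it through.** **The plan's own figures.** No event rate, hazard ratio or power is stated for this endpoint. The sample size (section 10.1) is for EQ-5D-5L and reproduces: difference 0.08, SD 0.240, two-sided alpha 0.025 and 80% power give 172 per arm by normal approximation and 173 with the exact t-test; 173/0.88 = 196.6, so 197; 3 × 197 = 591. The 197 is used below.

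**Direct reading of the rule (no assumptions).**

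- 5, 6, 7, 8, 9: weekly changes are +1, +1, +1, +1. Pain is 4 points up and there is no event.
- 8, 2, 4: changes are −6, +2. There is an event, with pain 4 points below baseline.

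**Simulation inputs.** From the protocol: 0–10 whole-number scale, entry score at least 4, 26 weekly comparisons. Assumed, because the protocol gives none: baseline mean 6.5 and SD 1.5, within-patient error SD s from 0.5 to 1.5, and week-to-week error correlation r of 0 or 0.5. A rise of at least 2 counts. There were 40,000 patients per setting.

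For a patient with no true change, the weekly difference has SD s√(2(1−r)) before rounding. Share with an event by week 26 under the protocol rule:

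| s | r | SD of weekly difference | No change | 2-point improvement over 6 weeks |
|---|---|---|---|---|
| 0.5 | 0 | 0.71 | 47% | 43% |
| 0.7 | 0 | 0.99 | 87% | 85% |
| 1.0 | 0 | 1.41 | 99% | 99% |
| 1.5 | 0 | 2.12 | >99% | >99% |
| 0.5 | 0.5 | 0.50 | 11% | 9% |
| 0.7 | 0.5 | 0.70 | 47% | 42% |
| 1.0 | 0.5 | 1.00 | 88% | 87% |
| 1.5 | 0.5 | 1.50 | 99% | >99% |

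The third column drives the result: settings with similar weekly-difference SDs give nearly the same event share. Whole-number scoring matters too. On an unrounded scale with s = 0.7 and r = 0, the weekly probability is 1 − Φ(2/0.99) = 0.0217, and 1 − (1 − 0.0217)^26 = 43%, against 87% with whole-number scores.

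**Timing.** Final proportions understate the contrast. At s = 1.0 and r = 0, events by week 6 are 67% (no change) versus 51% (improving), with median times of 4 and 6 weeks.

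**Log-rank power**, 197 per arm, two-sided 0.05, 300–400 replicates (Monte Carlo standard error at most √(0.25/300) = 0.029). The alternative event is PI-NRS at least 2 above baseline at two consecutive weeks.

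| Contrast with an unchanged arm | Protocol rule | Alternative |
|---|---|---|
| 2-point improvement over 6 weeks | 5–62% | 97–100% |
| 3-point improvement over 6 weeks | 10–94% | – |
| Steady 3-point worsening over 26 weeks | 4–33% | 100% |

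**True deterioration.** A steady 3-point worsening is 3/26 = 0.12 points a week. At s = 0.7 and r = 0, the protocol rule records events in 84% of worsening patients and 87% of stable ones. With baseline mean 6, SD 1.2 and s of 0.5–1.0, the ranges over both correlations are 17–99% (worsening) and 11–99% (stable). The alternative gives 89–96% and 5–40%.

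**Loss of response.** Take the same lower baseline, a 3-point response by week 6 and complete loss at week 13. The protocol rule records an event in about 99% of patients; the alternative records 3–31%.

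**Scope of MQS-III.** Section 6 covers all analgesics; section 10.3.3 explains the event as rescue medication; section 8.1 calls protocol gabapentin rescue medication. No section says whether pregabalin, gabapentin, lidocaine plaster or capsaicin given under the protocol enters the score.

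**The case against.** **Size.** The protocol gives no within-patient SD or correlation. At s = 0.5 with correlation 0.5 only about 11% of stable patients have an event. This stands, and the size must be given as a range.

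**Separation.** A reader might infer that the endpoint fills with noise in every arm and cannot tell an improving arm from an unchanged one. The documents do not support that. The analysis is time-to-event, early curves differ, and power reaches 62% for a 2-point gain and 94% for a 3-point gain.

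**MQS-III.** A reader might also infer that the medication event is biased against pregabalin by construction, because section 7.1.1 speaks of "any of the analgesic medications investigated in this trial" and section 6 scores all analgesics. That overreads a recruitment sentence, which is not a scoring rule and covers the topicals as well. Section 10.3.3 itself speaks of rescue medication, and study-drug dosing is documented separately (section 7.7). The MQS-III weights are not in the document. What remains is ambiguity, with gabapentin the most arguable case. Handling of a zero score alone could be left to an analysis plan; the missing reference and scope leave the stated event open to different readings.

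**Other analyses.** Pain is also compared by regression at weeks 6 and 26 and by mixed models. This stands and limits the consequences.

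**The alternative has its own blind spot.** It misses patients who respond and then return to baseline, and it cannot fire when baseline is 9 or 10. This stands and shapes the recommendation.

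**Conclusion.** The point holds in limited form. The pain event is badly fixed: it cannot register deterioration in 1-point steps, and it counts a single rebound in a patient far below baseline. Both follow from the wording alone.

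How far fluctuation dominates depends on assumptions. Most stable patients have an event at an SD of about 0.7 or more with uncorrelated error, or about 1.0 or more with correlation 0.5. In those settings the arms separate poorly, though not negligibly. The failure on gradual worsening is the firmest numerical result: power is 4–33% across all settings examined.

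The MQS-III event lacks a reference score, fails at zero and has unclear scope; a bias against pregabalin is possible but not established. The trial summary and section 10.3.3 disagree on the instruments. The primary analysis and sample size are unaffected. The definition should be corrected before analysis.

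**What to change.** In section 10.3.3:

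- Define pain worsening as PI-NRS at least 2 points above baseline at two consecutive weekly assessments, dated at confirmation.
- Keep the previous-assessment rule only as a sensitivity analysis.
- Report loss of response separately, with its own stated definition.
- Define medication worsening as a confirmed MQS-III rise of 30% over baseline, or any confirmed non-zero score if baseline is zero.
- State that MQS-III, both in this event and in the rescue-medication analysis, excludes pregabalin, gabapentin, lidocaine plaster and capsaicin given under the protocol.

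Align the trial summary with section 10.3.3 on PI-NRS, NPSI and MQS-III.

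The cost is wording only: the weekly scores and medication records are already collected. The price in the analysis is fewer events, dates that fall only at confirmation, and a main definition less sensitive to loss of response and unable to fire at baseline 9 or 10.
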